2.3. Plasma Glucose, Insulin, Cortisol and Glucagon Analysis

Blood samples of the participants were collected in EDTA tubes and centrifuged immediately after collection. Glucose, insulin, cortisol and CRP were measured in the same day in the laboratory at Marmara University Hospital. Glucose was measured by glucose hexokinase method (Cobas c701/702, Roche). Insulin and cortisol were measured by ECLIA (Cobas e801 Roche and e601 Roche, respectively. For glucagon samples, plasma was separated after centrifugation, and stored at 4°C until the OGTT was ended (180 min). Following the completion of OGTT, all glucagon samples were immediately stored at -80°C prior to shipment to the laboratory at Yeditepe University where glucagon assay was performed.

Plasma glucagon was measured by using a direct sandwich ELISA technique (Mercodia Glucagon ELISA, cat. no. 10-1271-01, lot no. 29870, Uppsala, Sweden) with standard manufacturer's protocol. Optical density (OD) values of the samples were read in ELISA plate reader at 450 nm wavelengths (EPOCH-Spectrophotometer, BioTek, USA). The concentrations of the samples were calculated according to the standard curve drawn based on the OD of the manufacturer's standards with known concentrations. Each sample was measured in two different wells for double-check.

Commercial controls pools with low, intermediate and high glucagon concentrations routinely assayed as samples.

THE EFFECT OF PANCREATIC INSUFFICIENCY ON HYPOGLYCEMIA AND GLUCAGON RESPONSE IN CHILDREN WITH CYSTIC FIBROSIS

Short Running Title: Hypoglycemia and Glucagon Response in CF

[name],PhD^{1,2} [name], MD¹ [name], PhD² [name], PhD² [name], MD¹ [name], MD¹ [name], MD¹ [name], MD³ [name], MD³ [name], MD³ [name], PhD² [name], MD¹

 ¹ Division of Pediatric Endocrinology and Diabetes, Department of Child Health and Disease, Marmara University School of Medicine, Istanbul, Turkey
² Department of Molecular Medicine, School of Health Science, Yeditepe University, Istanbul, Turkey

³ Division of Pediatric Pulmonogy, Department of Child Health and Disease, Marmara University School of Medicine, Istanbul, Turkey

Corresponding author: [name], [contact] [contact]

STATISTICAL ANALYSIS METHOD

All analyses were carried out using GraphPad Prism® V5.0 software (GraphPad Software Inc., San Diego, California, USA). Variables are summarized for each group using descriptive statistics as percentages and mean \pm SD. Pairwise comparisons were performed using the Student T test or the Mann-Whitney U test depending on the data's normality. Kolmogorov-Smirnov test was used to evaluate of the data normality. Data were expressed as mean and standard error or deviation, which was stated. Statistical significance was set at *p* < 0.05.

THE EFFECT OF PANCREATIC INSUFFICIENCY ON HYPOGLYCEMIA AND GLUCAGON RESPONSE IN CHILDREN WITH CYSTIC FIBROSIS

Short Running Title: Hypoglycemia and Glucagon Response in CF

[name],PhD^{1,2} [name], MD¹ [name], PhD² [name], PhD² [name], MD¹ [name], MD¹ [name], MD¹ [name], MD³ [name], MD³ [name], MD³ [name], PhD² [name], MD¹

 ¹ Division of Pediatric Endocrinology and Diabetes, Department of Child Health and Disease, Marmara University School of Medicine, Istanbul, Turkey
² Department of Molecular Medicine, School of Health Science, Yeditepe University, Istanbul, Turkey

³ Division of Pediatric Pulmonogy, Department of Child Health and Disease, Marmara University School of Medicine, Istanbul, Turkey

Corresponding author: [name], [contact] [contact]

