2.1. Participants

Children and adolescents aged 10-18 years with CF who were regularly followed-up at the Pediatric Pulmonology and Endocrinology Units, between January 2020 and December 2020 were invited to participate in the study before their annual OGTT. Pancreatic insufficiency (PI) was defined by need for enzyme replacement therapy based on clinical symptoms or fecal elastase level ($<200 \ \mu g/g$). Individuals using corticosteroid therapy, those who had acute exacerbation in the last 3 months or previously diagnosed with diabetes were not eligible. Height, weight, BMI, FEV1, genetics and the presence of PI of the participants were recorded.

The control group included age-matched healthy, non-diabetic siblings of patients with type 1 diabetes who were followed-up at our clinic. All the controls were negative for β -cell autoantibodies (anti-glutamic acid decarboxylase, islet cell antibody, and insulin antibody). The study protocol was approved by the Marmara University Ethics Committee (no:09.2019.933), and written informed consent was obtained from the parents and the participants.

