2.2. Procedures

A 3-h OGTT was performed in the morning following overnight fasting of ≥ 8 h. All participants (CF patients and controls) received oral glucose solution (1.75 g/kg; max: 75 g). Blood samples were collected at 0, 30, 60, 90, 120, 150 and 180 min for glucose and insulin, 0, 60, 120,150 and 180.min for glucagon measurement. HbA1c and CRP levels at baseline and cortisol levels at 0-180.min were also measured to assess the status of inflammation and body stress.

OGTT results were categorized into different subgroups of glucose tolerance according to ISPAD guidelines (12). Subjects who had INDET (Indeterminate Glucose Tolerance) or IGT (Impaired Glucose Tolerance) without hypoglycemia on OGTT were classified as Abnormal Glucose Tolerance (AGT). According to the IHSG position statement, hypoglycemia was defined in the presence of any venous glucose level is lower than 70 mg/dL (13). The terminology of "isolated hypoglycemia" (IsoHypo) was used for the participants who had hypoglycemia without AGT or CFRD and "Hypo+AGT" was used for the participants who had hypoglycemia with AGT. After the first analyses, the participants with IsoHypo and NGT were also sub-classified according to the presence of PI to evaluate the effect of PI on hypoglycemia (Figure-1).

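### The analysis section names only the Student t test or Mann-Whitney, chosen by a normality check; if group sizes and SDs differ together, the t test's 5% error rate is not protected, and Welch's test would protect it in near-normal data

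*Combined protocol and SAP*

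**What the plan says.** The Statistical Analysis Method section gives the whole two-group method in a few sentences. "Pairwise comparisons were performed using the Student T test or the Mann-Whitney U test", the choice resting on normality, and "Kolmogorov-Smirnov test was used to evaluate of the data normality". The threshold is given as "Statistical significance was set at *p* < 0.05". There is no variance check, no Welch or other unequal-variance test, and no statement of how unequal variances were handled.

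The groups compared come from sections 2.1 and 2.2. Patients seen "between January 2020 and December 2020 were invited to participate in the study before their annual OGTT". Then "OGTT results were categorized into different subgroups of glucose tolerance according to ISPAD guidelines". Finally, "After the first analyses, the participants with IsoHypo and NGT were also sub-classified according to the presence of PI". Controls are recruited separately; they are described as age-matched, but no matching ratio is given. No group size and no SD appears anywhere.

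**The concern.** The Student t test in its usual form pools the two variances. That is harmless when the SDs are equal and nearly harmless when the group sizes are. When both differ, the pooled estimate is dominated by the larger group. If the smaller group is the more variable, the standard error is too small and too many differences are declared. If the larger group is, the standard error is too large and real differences are missed.

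Nothing in this design sets the group sizes: they are whatever the year's OGTT results and PI status produce. Nothing makes the SDs equal either. The only safeguard in the plan, the Kolmogorov-Smirnov check, looks at the shape of the data and not at the ratio of the SDs. The group contrasts in glucose, insulin and glucagon are how the study addresses the mechanism of hypoglycemia, so a p value that does not mean what it says affects the main conclusions.

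**Working it through.** **Inputs.** From the documents: a 5% threshold; Student t or Mann-Whitney, chosen by Kolmogorov-Smirnov. Assumed: two-sided testing (sidedness is not stated), pooled variance (the conventional reading of Student t), normal data, and all group sizes and SD ratios. The rule was simulated as Mann-Whitney if Kolmogorov-Smirnov rejects at 5% in either group, otherwise pooled t.

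**Step 1: recover the nominal figure.** With equal SDs, simulation gives 4.9-5.1% for the t test and 5.0-5.2% for the rule. The stated 5% is reproduced, but only by assuming equal SDs.

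**Step 2: hand check of the pooled t test.**

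- True variance of the mean difference: V = s1²/n1 + s2²/n2.
- Variance the pooled test expects: P = [((n1−1)s1² + (n2−1)s2²)/(n1+n2−2)] × (1/n1 + 1/n2).
- The test statistic is stretched by k = √(V/P), so the error is about 2 × [1 − Φ(1.96/k)].

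For 8 v 25 with the smaller group's SD twice the other's:

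- V = 4/8 + 1/25 = 0.540.
- P = [(7×4 + 24×1)/31] × (1/8 + 1/25) = 1.677 × 0.165 = 0.277.
- k = √(0.540/0.277) = 1.40, so the error is about 16%.

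The same formulas for other cases:

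| Sizes | SDs (first v second group) | V | P | k | Approximate error |
|---|---|---|---|---|---|
| 8 v 25 | 1.5 v 1 | 0.321 | 0.212 | 1.23 | 11.2% |
| 8 v 25 | 2 v 1 | 0.540 | 0.277 | 1.40 | 16% |
| 8 v 25 | 1 v 1.5 | 0.215 | 0.325 | 0.81 | 1.6% |
| 8 v 25 | 1 v 2 | 0.285 | 0.548 | 0.72 | 0.7% |
| 12 v 15 | 1.5 v 1 | 0.254 | 0.233 | 1.05 | 6.1% |
| 15 v 15 | 2 v 1 | 0.333 | 0.333 | 1.00 | 5.0% |

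**Step 3: simulation of the whole rule.** Equal means, at least 40,000 runs per case (simulation error 0.1-0.2 points):

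| Sizes | SDs | Rule | Mann-Whitney alone |
|---|---|---|---|
| 8 v 25 | 1.5 v 1 | 10.8-11.0% | 7.9% |
| 8 v 25 | 2 v 1 | 15.5-15.7% | 10.0% |
| 8 v 25 | 1 v 1.5 | 1.9-2.0% | 2.8% |
| 8 v 25 | 1 v 2 | 0.9-1.0% | 2.0% |
| 10 v 20 | 2 v 1 | 11.5-11.6% | about 8.5% |
| 10 v 20 | 1 v 2 | 1.8-2.1% | about 3.2% |
| 12 v 15 | 1.5 v 1 | 6.2% | 5.6% |

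At 15 v 15 with unequal SDs the rule stays close to 5% (5.0-5.7% over repeated runs). Welch's test stays at 4.8-5.4% in all of these settings.

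**Step 4: does the normality check catch it?** Applied per group to normal data, with the estimated mean and SD allowed for, the check sent 9.6-10.1% of datasets to Mann-Whitney, whether the SDs were equal or differed threefold. Applied to the two groups pooled, it rejected 7-14% at an SD ratio of 2, against 5% with equal SDs, and still left the rule at 14.1% for 8 v 24. It is essentially blind to unequal SDs.

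**The case against.** **No defect is demonstrated.** Two unknowns must occur together, unequal sizes and unequal SDs, and the documents give neither. Age-matched controls could be near-equal in number to the patients, and at mild imbalance the departure is small. This stands. A reader might infer that the study's p values are inflated; the documents do not support that, because with the larger group more variable the same rule is conservative.

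**The one design-based reason for unequal SDs is weak.** Groups cut at different glucose limits may well have different glucose SDs, but at the defining time points equal mean glucose is false by construction, so a false-positive rate means little there. For the hormones, and for PI v no PI, equal SDs are simply not assured. This also stands, and it keeps the point to an unprotected assumption.

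**Mann-Whitney is a valid test.** A reader might infer that neither permitted test holds 5%. That is too strong: Mann-Whitney keeps its level as a test of identical distributions. Only when it is read as a test of equal means or medians does it depart from 5%, and then by less than the t test. The section summarises data as means, so that reading is a natural one.

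**Pooled variance is an interpretation.** The section says Student t and no more. Pooling is the conventional meaning, but what the text firmly supports is that the handling of unequal variances is not stated.

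**Conclusion.** The concern holds as a modest, inexpensive improvement to consider. The plan's test menu leaves the 5% level dependent on equal SDs or equal group sizes, neither of which the design assures, and its normality check would not reveal a problem. In normal data the t test's error could plausibly lie anywhere from about 1% to about 16% under strong imbalance (8 v 25, SD ratio up to 2). It is about 6% under mild imbalance (12 v 15, ratio 1.5) and about 5% when either sizes or SDs are equal. Every size and ratio behind these figures is an assumption. Whether any comparison in this study is affected, and in which direction, cannot be told from the documents; the investigators can tell from their own data.

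**What to change.** Make Welch's unequal-variance t test the default for comparisons of means, in place of choosing between pooled t and Mann-Whitney by a normality pre-test. Use the same method at every time point of a given variable, and report each mean difference with its 95% confidence interval. Mann-Whitney may stay as a sensitivity analysis, described as a comparison of distributions and not of means. Listing the size and SD of each group beside each comparison would let readers see whether the choice mattered.

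The work is a change of wording and a re-run on existing data. Patients were invited in 2020 and the document is dated 30/12/2022, so the re-run should be labelled as a revised analysis.

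The statistical cost is some power if the SDs are in fact equal. For normal data and a true difference of 1 SD, power falls from about 66% to 62% at 8 v 25, from 70% to 68% at 10 v 20, and hardly at all at 15 v 15 (75.4% to 75.2%). Welch's test is also not exact under strong skew in small unequal groups: in one severe assumed log-normal case (8 v 25, log SD 0.8 in the smaller group and 0.4 in the larger, equal means) its error reached about 12%. It should therefore not be presented as a complete remedy for heavily skewed variables.
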